Cycle 1:

Ublituximab			Umbralisib	Acalabrutinib
Day 1	Day 2	Day 8 & 15	Daily	Every 12 hours
150 mg	750 mg	900 mg	800 mg	previously tolerated dose

[figure not shown]
Cycles 2 through 6:

Ublituximab	Umbralisib	Acalabrutinib
Day 1	Daily	Every 12 hours
900 mg	800 mg	previously tolerated dose

Cycles 7-24:

Ublituximab	Umbralisib	Acalabrutinib
Day 1 of Cycles 9, 12, 15, 18, 21 and 24	Daily	Every 12 hours
900 mg	800 mg	previously tolerated dose

Study Schema - Re-Treatment

*Progression Of Disease (PD) – Defined per the iwCLL Criteria (Hallek 2018)

U2 – ublituximab and umbralisib; IB – ibrutinib; ACALA – Acalabrutinib; VEN – venetoclax; MRD – minimal residual disease; EOS – end of study

Retreatment will start with 2 cycles of single agent treatment with ibrutinib, acalabrutinib or venetoclax per the subject's history on study. Umbralisib and ublituximab will be started in Cycle 3 of re-treatment. Subjects will again be evaluated with serial peripheral blood MRD analysis. If subjects achieve U-MRD status in the peripheral blood, MRD will again be assessed by peripheral blood 4 weeks later to confirm U-MRD. Retreatment will continue until the occurrence of confirmed U-MRD response in the peripheral blood, completion of 26 cycles (24 cycles of triplet therapy), definitive disease progression, unacceptable toxicity, or withdrawal from the study due to investigator decision or other reasons. Subjects who discontinue study treatment and have not progressed will continue to be followed for disease progression.

Re-treatment schedule as follows:

Cohort A: Ublituximab and Umbralisib with Ibrutinib

Cycles 1 and 2:

Ibrutinib				
Daily				
Daily at previously tolerated dose. Investigator discretion may be used to start subjects at a higher dose than last tolerated (maximum dose 420mg daily).				

Cycle 3:

Ublituximab			Ibrutinib	Umbralisib
Day 1	Day 2	Day 8 & 15	Daily	Daily
150 mg	750 mg	900 mg	At appropriate dose based on initial protocol treatment	Previously tolerated dose. Investigator discretion may be used to start subjects at a higher dose than last tolerated (maximum dose 800mg daily).

Cycles 4 through 8:

Ublituximab	Ibrutinib	Umbralisib
Day 1	Daily	Daily
900mg	At appropriate dose based on previous Cycle	At appropriate dose based on previous Cycle

Cycle 9 through Cycle 26:

Ublituximab	Ibrutinib	Umbralisib
Day 1 of Cycle 11, 14, 17, 20, 23 & 26	Daily	Daily
900 mg	At appropriate dose based on previous Cycle	At appropriate dose based on previous Cycle

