Cohort C: Ublituximab and Umbralisib with Acalabrutinib																				
Cycle 1:																				

  
 Ublituximab	Umbralisib	Acalabrutinib	
 
 Day 1	Day 2	Day 8 & 15	Daily	Every 12 hours	
   
 150 mg	750 mg	900 mg	800 mg	previously tolerated dose	
  
						Ublituximab		Umbralisib	Acalabrutinib		Day 1	Day 2	Day 8 & 15	Daily	Every 12 hours	150 mg	750 mg	900 mg	800 mg	previously tolerated dose
Ublituximab		Umbralisib	Acalabrutinib																	
Day 1	Day 2	Day 8 & 15	Daily	Every 12 hours																
150 mg	750 mg	900 mg	800 mg	previously tolerated dose																
Cycles 2 through 6:																				

  
 Ublituximab	Umbralisib	Acalabrutinib	
   
 Day 1	Daily	Every 12 hours	
 
 900 mg	800 mg	previously tolerated dose	
  
						Ublituximab	Umbralisib	Acalabrutinib	Day 1	Daily	Every 12 hours	900 mg	800 mg	previously tolerated dose						
Ublituximab	Umbralisib	Acalabrutinib																		
Day 1	Daily	Every 12 hours																		
900 mg	800 mg	previously tolerated dose																		
Cycles 7-24:																				

  
 Ublituximab	Umbralisib	Acalabrutinib	
   
 Day 1 of Cycles 9, 12, 15, 18, 21 and 24	Daily	Every 12 hours	
 
 900 mg	800 mg	previously tolerated dose	
  
						Ublituximab	Umbralisib	Acalabrutinib	Day 1 of Cycles 9, 12, 15, 18, 21 and 24	Daily	Every 12 hours	900 mg	800 mg	previously tolerated dose						
Ublituximab	Umbralisib	Acalabrutinib																		
Day 1 of Cycles 9, 12, 15, 18, 21 and 24	Daily	Every 12 hours																		
900 mg	800 mg	previously tolerated dose																		
Study Drugs	Ublituximab is a recombinant chimeric monoclonal antibody against the CD20 antigen, available as a 25 mg/mL concentrate for solution for infusion, supplied by TG Therapeutics, Inc.																			

Umbralisib is a highly specific and orally available dual inhibitor PI3K delta (δ) and CK-1 epsilon available in 200 mg tablets, supplied by TG Therapeutics, Inc.

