5.4 RETREATMENT PHASE

Study Schema for Re-Treatment

*Progression Of Disease (PD) – Defined per the iwCLL Criteria (Hallek 2018)
U2 – ublituximab and umbralisib; IB – ibrutinib; ACALA – Acalabrutinib; VEN – venetoclax; MRD – minimal residual disease; EOS – end of study

Subject on treatment-free observation who subsequently develop clinical progression requiring treatment per iwCLL criteria (Hallek, et al., 2018) after 6 months of treatment-free observation will be retreated with the triple combination regimen that was previously received. Subjects who progress within 6 months of treatment-free observation discontinue from the study.

For subjects enrolled in Cohort A, retreatment will consist of 2 cycles of ibrutinib followed by treatment with ublituximab and umbralisib with ibrutinib cycles 3 through 26 of retreatment. The previously tolerated ibrutinib dose should be considered but is at investigator discretion (maximum dose 420mg daily).

For subjects enrolled in Cohort B, venetoclax should be initiated per the package insert. The target ramp-up dose should be considered based on the previously tolerated dose but is at investigator discretion (maximum dose 400mg daily). Retreatment will consist of 2 cycles of venetoclax followed by treatment with ublituximab and umbralisib with venetoclax cycles 3 through 26.

For subjects enrolled in Cohort C, retreatment will consist of 2 cycles of acalabrutinib followed by treatment with ublituximab and umbralisib and acalabrutinib cycles 3 through 26 of retreatment. The previously tolerated acalabrutinib dose should be considered but is at the investigator discretion.

Clinical response and U-MRD rate will be studied upon retreatment. If subjects achieve U-MRD status in the peripheral blood, MRD will be assessed by peripheral blood 4 weeks later to confirm U-MRD. Retreatment will continue until the occurrence of confirmed U-MRD response in the peripheral blood, completion of 26 cycles (24 cycles of triplet therapy), UTX-TGR-208

Version 2.0 Dated: 30 July 2020

definitive disease progression, unacceptable toxicity, or withdrawal from the study due to investigator decision or other reasons. Subjects who discontinue study treatment and have not progressed will continue to be followed for disease progression.

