5.5 RESPONSE ASSESSMENT RE-TREATMENT

Tumor assessment will be performed cycles 7, 14, 20 and 26 then every 12 months. Best clinical response and disease progression will be investigator assessed.

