7.3 STUDY ASSESSMENT AND TREATMENT SCHEDULE – RE-TREATMENT

Cycle=28 days	Screen	Cycle 1 ¹				Cycle 2 ²		Cycle 3 ³				Cycles 4-8 ⁴		C11-C26 ⁵	EOS ⁶	LTFU
Procedures/Days	D-28 to D1	D1	D8 ⁶	D15 ⁷	D22 ⁷	D1	D8 ⁷	D1	D2	D8	D15	D1	D1 every 3 Cycles			
Physical Examination	X	X				X		X				X	X	X		
ECOG PS	X	X				X		X				X	X	X		
Vital Signs ⁸	X	X	X	X	X	X	X	X	X	X	X	X	X	X		
12-Lead EKG	X															
Hematology	X	X	X	X	X	X	X	X	X	X	X	X	X	X	X	
Chemistry	X	X	X	X	X	X	X	X	X	X	X	X	X	X	X	
Coagulation Studies	X	X				X		X					X	X		
HCV, HBV, CMV ⁹	X															
CMV surveillance ¹⁰								X				C6&8	C11, 14, 17 etc			
MRD-PB ¹¹	X											X ²⁶	X ²⁶			
β ₂ -microglobulin	X															
Pregnancy Test ¹³	X					X		X				X	X			
Response Assessments ¹⁴	X											C7	X ¹⁵		X ¹⁶	
Tumor Lysis Risk Assessment ¹⁷		X														
AE Assessment	X	X	X	X	X	X	X	X	X	X	X	X	X	X	X	
Con Meds	X	X	X	X	X	X	X	X	X	X	X	X	X	X	X	
Ublituximab ¹⁸								X	X	X	X	X	X	X	X	
Umbralisib ¹⁹												Daily until confirmed U-MRD				
Cohort A: Ibrutinib ²⁰												Daily until confirmed U-MRD				
Cohort B: Venetoclax ²¹												Dose ramp-up as per package insert and daily until confirmed U-MRD				
Cohort C: Acalabrutinib												Every 12 hours until confirmed U-MRD				

¹ Treatment Administration +/- 1 day window after cycle 1 day 1. Physical Exam, Vital Signs, ECOG PS, Hematology and Serum Chemistry visit days have - 1 day window. All assessments must be completed prior to treatment.

² Treatment Administration +/- 3 day window. Physical Exam, Vital Signs, ECOG PS, Hematology and Serum Chemistry visit days have a - 3 day window during Cycles 2 through 6.

³ Treatment Administration +/- 7 day window. Physical Exam, Vital Signs, ECOG PS, Hematology and Serum Chemistry visit days have a - 7 day window.

⁴ Treatment Administration +/- 3 day window. Physical Exam, Vital Signs, ECOG PS, Hematology and Serum Chemistry visit days have a - 3 day window during Cycles 2 through 6.

⁵ Day 1 every 3 Cycles (Cycle 11, 14, 17, 20, 23, 26): Treatment Administration +/- 7 day window. Physical Exam, Vital Signs, ECOG PS, Hematology and Serum Chemistry visit days have a - 7 day window.

⁶ Cycle 1 Days 8, 15 & 22 assessments only for subjects receiving venetoclax.

⁷ Cycle 2 Day 8 assessments only for subjects receiving venetoclax.

⁸ Vital signs to include temp, BP, HR, respirations and weight (weight only at baseline).

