⁹ Serum Virology to include HBsAg, HBC antibody, HCV antibody, CMV IgG and CMV IgM or CMV by PCR. If HBC antibody is positive, the subject must be evaluated for the presence of HBV DNA by PCR - See Appendix D. If the subject is CMV IgG or CMV IgM positive, the subject must be evaluated for the presence of CMV DNA by PCR.

¹⁰ CMV surveillance by PCR every 3 cycles while receiving study treatment. In addition, a final CMV test by PCR should be done upon treatment discontinuation if not already done within previous 3 months.

¹¹ For retreatment, MRD analysis should be done within 30 days of restarting therapy in peripheral blood (PB) then performed Cycles 6, 8, 11, 14, 17, 20, 23, and 26. If U-MRD in PB during retreatment repeat approximately 4 weeks later. If U-MRD confirmed approximately 4 weeks later, discontinue treatment and follow for progression and survival for 24 months.

¹³ For women of childbearing potential: Serum pregnancy test within 3 days prior to Cycle 1/Day 1; Urine pregnancy tests on Day 1 of each treatment cycle +/- 7 days.

¹⁴ Radiology assessment should include contrasted CT or MRI imaging of neck, chest, abdomen, and pelvis. Scans to be completed within 30 days prior to Cycle 1/Day 1.

¹⁵ Re-treatment subjects – radiology and response assessment within 14 days of Cycles 7, 14, 20, 26 then every 12 months thereafter. At the time of response assessment, bone marrow to be performed as per standard of care if other criteria for complete remission are met. CR should only be confirmed once by bone marrow assessment at planned response assessments.

¹⁶ Response Assessment to be done as per SOC to determine progression-free survival

¹⁷ For subjects being re-treated with venetoclax only. Refer to section 8.3.5.1

¹⁸ Ublituximab Cycle 3 Days 1,2, 8 & 15; Cycle 4-8 Day 1 then every 3 cycles (C11, C14, C17, C20, C23, C26). No further ublituximab after cycle 26

¹⁹ When starting retreatment, dose of umbralisib is at the investigator's discretion, previously tolerated dose should be considered.

²⁰ When starting retreatment, dose of ibrutinib or acalabrutinib is at the investigator's discretion, previously tolerated dose should be considered.

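### The synopsis Cohort C re-treatment table repeats the initial-treatment schedule, and one criterion in Section 8.3.6 contradicts the re-treatment stopping rules

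*Combined protocol and SAP*

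**What the plan says.** **(a) Cohort C re-treatment schedule.** The synopsis text on re-treatment describes two single-agent cycles for all three cohorts, then says: "Umbralisib and ublituximab will be started in Cycle 3 of re-treatment". The Cohort A and B tables that follow agree. The Cohort C table does not. Its rows are Cycle 1, Cycles 2 to 6 and Cycles 7 to 24, with the triplet from Cycle 1, umbralisib at 800 mg and late ublituximab on "Day 1 of Cycles 9, 12, 15, 18, 21 and 24". Those rows match the Cohort C initial-treatment tables in the synopsis and in Section 8.1, where they are correct.

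Section 5.4 states for Cohort C that "retreatment will consist of 2 cycles of acalabrutinib followed by treatment with ublituximab and umbralisib and acalabrutinib cycles 3 through 26 of retreatment". Section 7.3 (ublituximab row and footnote 18) and Section 8.2 give the same timing. The rules on interrupted infusions (8.3.1.1), flow rates (8.3.1.2), dilution (8.3.1.3.1) and prophylaxis (8.3.2) all treat re-treatment Cycle 3 as the start of ublituximab or umbralisib.

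**(b) When re-treatment stops.** The synopsis says, and Section 5.4 repeats: "Retreatment will continue until the occurrence of confirmed U-MRD response in the peripheral blood, completion of 26 cycles (24 cycles of triplet therapy"; progression, toxicity and withdrawal are listed as further reasons. In Section 7.3 the oral-drug rows run to confirmed U-MRD (for acalabrutinib, "Every 12 hours until confirmed U-MRD"), footnote 11 stops treatment on confirmed U-MRD, and footnote 18 allows no ublituximab after Cycle 26. Section 8.3.6 lists conditions for continuing. One item is met if the subject is D-MRD or is still short of 26 completed cycles.

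**The concern.** One is a dosing table and the other a continuation rule, so following either as printed would give wrong treatment.

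Under the table, a Cohort C subject would restart all three drugs together, with no lead-in. Umbralisib would be at a printed 800 mg, where Section 8.2 asks for the previously tolerated dose in Cycle 3. The Section 7.3 visits are built around a Cycle 3 start, so dosing days and visit days would no longer match. Blood counts bear on dosing, because Table 2 in Section 8.4.1 delays ublituximab for Grade 4 neutropenia or thrombocytopenia. MRD samples and response assessments are fixed by cycle number, so they would be read after a different amount of triplet treatment than in Cohorts A and B.

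Under the criterion in 8.3.6, a subject could be kept on treatment after the protocol's own stopping point.

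At stake are safety monitoring and the secondary re-treatment objective in Section 3.1. The primary U-MRD rate comes from initial treatment.

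**Working it through.** No sample size or error rate is involved. The inputs are the synopsis, 5.4, 5.5, 7.3, 8.2 and 8.3.6. Days are nominal, cycles are 28 days, visit windows are ignored, and an assessment in Cycle k is taken at its Day 1.

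**1. Dose and timing**

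| | Synopsis table | Section 8.2 | Infusions | mg |
|---|---|---|---|---|
| Split first dose, Days 1, 2, 8, 15 | Cycle 1 | Cycle 3 | 4 | 150 + 750 + 900 + 900 = 2,700 |
| Day 1, five cycles | Cycles 2–6 | Cycles 4–8 | 5 | 5 × 900 = 4,500 |
| Day 1, every third cycle | 9, 12, 15, 18, 21, 24 | 11, 14, 17, 20, 23, 26 | 6 | 6 × 900 = 5,400 |
| Total | | | 15 | 12,600 |

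Adding 2 to every cycle number in the synopsis table gives Section 8.2 exactly. The triplet would start 2 × 28 = 56 days early, and the ublituximab total is the same.

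**2. Infusions against Section 7.3 visits**

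The Cohort C visit columns are C1 D1; C2 D1; C3 D1, D2, D8 and D15; D1 of C4–8; and D1 of C11, 14, 17, 20, 23 and 26. The extra early visits do not apply: "Cycle 1 Days 8, 15 & 22 assessments only for subjects receiving venetoclax", and the Cycle 2 Day 8 visit carries the same limit.

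- Synopsis table: no column for C1 D2, D8 and D15 or for C9, 12, 15, 18, 21 and 24. That is 3 + 6 = 9 of 15 infusions with no scheduled hematology or chemistry. The six late doses each fall 28 days after the last column (C9 after C8, C12 after C11, and so on).
- Section 8.2: 0 of 15.
- Physical examination: the 7.3 row is marked on C3 D1 but blank on C3 D2, D8 and D15. The contrast is therefore 9 of 15 against 3 of 15.

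**3. Assessments against triplet exposure**

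MRD is tested at screening, "then performed Cycles 6, 8, 11, 14, 17, 20, 23, and 26". For response, "Tumor assessment will be performed cycles 7, 14, 20 and 26 then every 12 months". Triplet cycles completed before Cycle k are k − 1 under the table and k − 3 under Section 8.2.

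- Cycle 6 MRD: 6 − 1 = 5 against 6 − 3 = 3.
- Cycle 7 response: 7 − 1 = 6 against 7 − 3 = 4.
- Cycle 26 MRD and response: after the last treatment cycle (24) under the table, within treatment under Section 8.2.

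**4. Section 8.3.6 against the stopping rule**

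| MRD state | 26 cycles completed | Stopping rule | 8.3.6 as printed |
|---|---|---|---|
| D-MRD | no | continue | continue |
| D-MRD | yes | stop | continue |
| Confirmed U-MRD | no | stop | continue |
| Confirmed U-MRD | yes | stop | stop |

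The printed criterion agrees in 2 of 4 states. Requiring no confirmed U-MRD and fewer than 26 completed cycles agrees in 4 of 4.

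**The case against.** The strongest reply is that nobody should be misled. The text before the synopsis table names acalabrutinib in the lead-in, and the Treatment Plan and visit schedule are right on lead-in and timing. The monitoring gap arises only if a site doses from the synopsis and schedules visits from Section 7.3, which prints the correct ublituximab days. Section 8.4 also asks for clinical toxicity assessment at each visit, and an infusion attendance can be read as a visit. All of this stands. It limits the likely harm but leaves a dosing table that contradicts its own document.

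On 8.3.6, the lead-in refers back to the protocol. That softens the conflict, but the listed item still says the opposite of the stopping rule in two states.

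A reader might infer more than the documents support:

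- *That nine infusions lose a physical examination they would otherwise have.* Three infusions lack one on the correct schedule too, on the matching days of Cycle 3. Initial treatment follows the same pattern in Section 7.1.
- *That Section 7.3 already stops a D-MRD subject at Cycle 26.* Footnote 18 caps ublituximab only, and the oral-drug rows and footnote 11 depend on U-MRD. The explicit 26-cycle limit on all treatment is in the synopsis and Section 5.4.
- *That 8.3.6 would in practice cause long over-treatment after confirmed U-MRD.* Footnote 11 and the drug rows direct otherwise, so this is a contradiction to remove and not an expected event.
- *That a printed 800 mg of umbralisib breaches the re-escalation bar in Section 8.4.2.* Section 8.2 lets the investigator restart above the last tolerated dose, up to 800 mg, and the figure is probably nominal, as in Section 8.1. Whether the bar applies at re-treatment is unclear, but no error is shown.

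**Conclusion.** Both errors are in the current text and should be fixed. The intended Cohort C schedule is not in doubt, so the table is a mistake and not an alternative design.

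Its size, if the table were followed, is a triplet start 56 days early with the ublituximab total unchanged. The monitoring figures (9 against 0 of 15 infusions without scheduled hematology or chemistry, 9 against 3 without a scheduled examination) hold only if visits stay on Section 7.3. The shift in assessments (5 and 6 completed triplet cycles in place of 3 and 4) assumes that they keep their printed cycle numbers.

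The table reaches only Cohort C subjects who progress, need treatment and are re-treated after 6 months of treatment-free observation. The criterion in 8.3.6 reaches re-treated subjects in all cohorts. The primary endpoint and its analysis are not affected.

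**What to change.** **Synopsis.** Replace the Cohort C re-treatment table with the Section 8.2 schedule, and notify sites:

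- Cycles 1–2: acalabrutinib alone.
- Cycles 3–26: the triplet, with umbralisib restarted in Cycle 3 at the previously tolerated dose, maximum 800 mg.
- Ublituximab: Cycle 3 Days 1, 2, 8 and 15; Day 1 of Cycles 4–8; Day 1 of Cycles 11, 14, 17, 20, 23 and 26.

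**Section 8.3.6.** Reword the item as: *no confirmed U-MRD, and fewer than 26 re-treatment cycles completed*. Changing or to and is not enough, because it would stop treatment at a first U-MRD result, before the 4-week repeat.

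**Minor alignment.** In Section 8.2, Cohort C, Cycles 4–26, replace the printed umbralisib 800 mg with the dose carried over from the preceding cycle, as for Cohorts A and B.

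The cost is amendment wording and one site notice, with no new procedures or analyses.

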2 INTRODUCTION

2.1 CHRONIC LYMPHOCYTIC LEUKEMIA

Chronic Lymphocytic Leukemia (CLL) accounts for approximately 191,000 cases and 61,000 deaths worldwide each year (Global Burden of Disease Cancer Collaboration, 2017). CLL affects mainly older adults, accounts for one third of all diagnosed cases of leukemia, and is characterized by the accumulation of clonal mature B lymphocytes in the blood, bone marrow, and secondary lymphoid tissues (Lin K, 2002). CLL is a heterogeneous disease, with several higher risk cytogenetic abnormalities which are generally more difficult to treat, including 17p deletion, *TP53* gene mutation, and 11q deletion (Hallek, et al., 2008) (Lin K, 2002). Subjects with 17p deletion show higher resistance to conventional chemotherapy, as well as shorter duration of survival than non 17p deletion subjects. Subjects with 11q deletion have been associated with marked lymphadenopathy (Hallek, et al., 2008). Subjects with *TP53* mutations are associated with adverse clinical outcomes (Lin K, 2002).

Historically, chemotherapy regimens in combination with monoclonal antibody therapy had been standard of care for subjects with CLL. However, novel targeted agents have entered the marketplace and improved clinical outcomes for subjects with CLL. Frontline chemotherapeutic options for subjects with CLL include an anti-CD20 monoclonal antibody in combination with either fludarabine and cyclophosphamide or bendamustine. Depending on the age and comorbidities of the patient, chlorambucil is also considered, though its use within the US has been limited. Ibrutinib, a Bruton's tyrosine kinase (BTK) inhibitor, is approved in the front-line setting based on a randomized phase III trial demonstrating superior overall response rate (ORR), progression free survival (PFS), and overall survival (OS) as compared to chlorambucil (Barr, 2016). Acalabrutinib, another Bruton's tyrosine kinase (BTK) inhibitor, was approved by the FDA in the front-line setting for the treatment of subjects with CLL based on safety and efficacy data from two phase III trials (<https://www.calquence.com/cll.html>). Venetoclax, a BCL-2 inhibitor, either as monotherapy or in combination with rituximab, was approved by the FDA for the treatment of subjects with CLL in the relapsed or refractory setting (<https://www.rxabbvie.com/pdf/venclexta.pdf>).

Despite these advancements in available therapies, CLL remains an incurable disease, and many subjects will progress and eventually die from their disease. While novel agents including ibrutinib, acalabrutinib, and venetoclax have shifted the paradigm of CLL management, these agents are generally administered with a treat-to-progression approach under the current dosing guidelines, and depth of response is variable. Furthermore, subjects with higher risk cytogenetic abnormalities still present with a less than optimal response to approved therapies with shorter duration of response and shorter progression free survival. As such, there is a pressing need for new, innovative, targeted therapies for the treatment of subjects with relapsed or refractory CLL, especially those with cytogenetic abnormalities.

To address these needs, many studies evaluating combinations of three or four agents are underway. While combination treatment approaches are certainly appropriate in some cases, utilizing these approaches broadly may lead to overtreatment in some subjects who would have achieved deep response with a single agent. This study is designed to address these unmet needs in the treatment landscape of CLL.

